4.8.2. Safety laboratory data

Individual data listings of laboratory results will be presented for each subject. Flags will be attached to values outside of the laboratory's reference limits along with the Investigator's assessment. Clinically significant laboratory test abnormalities that were considered AEs by the Investigator will be presented in the AE listings.

Laboratory data will be summarized by type of laboratory test after all results are converted to standard SI units (according to algorithms presented in Data Validation Plan). Descriptive statistics will be calculated for each laboratory parameter at baseline (Day 1) and at each scheduled time point. Shift tables using the categories 'lower than normal range', 'within normal range' and 'higher than normal range' will be provided for each numeric parameter, comparing the baseline value to all post-baseline values. For results expressed as category (in urinalysis) shift tables will present categories: normal and abnormal. Moreover, change from baseline values will also be presented.

Other urinalysis parameters, than those pre-specified in the eCRF, will be listed only.

4.8.3. Other safety data

4.8.3.1. Vital signs

These summaries will take form of tables for raw data and changes from baseline (Day 1) as well as percentage of abnormal values.

Shift tables using the categories 'lower than normal range', 'within normal range' and 'higher than normal range' will be provided for each parameter (where applicable), comparing the baseline value to all post-baseline values. Categorization of blood pressure is performed for both SBP and DBP at once, so one shift table will be prepared only for blood pressure.

Change from baseline values in vital signs will take form of boxplots (and/or point and whisker plots) for each study arms for each vital sign parameter.

Listings flagging abnormal values will be also produced.

4.8.3.2. Electrocardiograms

ECG variables that will be analyzed include heart rate, ECG finding, PR, QRS, RR, QT and QTcF value.

ECG summaries will take form of tables for raw data and changes from baseline (values collected during Day -1 visit) as well as percentage of abnormal values. In addition, shift tables presenting number of patients that either developed abnormalities in PR, QRS, RR, QT and QTcF value (or had such abnormalities subsume) since baseline will be provided.

The number of patients with at least one clinically relevant finding detected during the ECG examination will be summarized in frequency tables for each scheduled assessment or visit.

Change from baseline values of ECG parameters will take form of boxplots for each study arms.

4.8.3.3. Physical examination

Abnormal findings occurring after screening and baseline visit (after Day 1) will be listed. No summaries beside baseline are planned.

4.8.3.4. Neurological, ophthalmological, dermatological

examination

Results of such examination will be listed only. No summaries are planned.

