Pharmacokinetic parameters of CPL500036 will be listed and summarized.

Pharmacokinetic/PD data will also be displayed graphically as appropriate.

[figure not shown]
Safety Analyses:

Evaluation of Safety endpoints will be summarized descriptively by treatment group and visit for the Safety Population.

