3.3.2. Safety

Secondary Endpoints:

- Physical, neurological, ophthalmological, and dermatological examination findings.
- Adverse event assessments.
- Hematologic, clinical chemistry, coagulation and urinalysis results.
- Electrocardiogram (ECG) results.
- Extrapyramidal side effects monitoring using the Extrapyramidal Symptom Rating Scale (ESRS).

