10.11.5. Physical Examination

Abnormal physical examination findings will be listed.

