10.11.6. Other Safety Variables

Abnormal neurological, ophthalmological and dermatological examinations findings will be listed.

Descriptive statistics of the score and change from baseline will be summarized at each scheduled time point for extrapyramidal side effects - ESRS scale.

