4.3. Demographics and baseline characteristics

Demographic data and other baseline characteristics will be summarized for Safety, FAS, PP and PSPC population by treatment group and overall. The following variables will be summarized:

- Age (years) as continuous variable [(date of ICF signature date of birth)/365.25]
- Race/ethnicity (White vs Other).
- Sex (male / female)
- Body weight without shoes [kg] and height without shoes [cm] at screening and baseline
- BMI [kg/m²] calculated as Weight (kg)/[height (m²)] at screening and baseline.

Weight, height and BMI will be shown both for screening and baseline (Day -1) visit.

Disease characteristic will summarize:

- Duration of disease [years]
- Duration of current exacerbation [days]

- Screening and baseline PANSS score as continuous variable (positive subscale, negative subscale, general psychopathology subscale, total score, Marder 5-factor model subscales)
- Screening and baseline PANSS score as category (low <95, high ≥95)
- Screening and baseline CGI-S items as numerical variable
- Baseline BACS T-score as continuous variable for each task and a composite value.

Separate table will present descriptive statistics for ESRS subscales.

A table will present descriptive statistics for vital signs measured during Screening and Baseline (Day -1) visit: blood pressure [mmHg], heart rate [beats per minute], respiratory rate [breaths per minute], body temperature [°C]. Blood pressure and heart rate will be presented for three time points:

- after 3 minutes lying down
- after 3 minutes sitting, immediately upon standing
- after 3 minutes standing.

Physical examination table will combine results from screening and baseline – in case of new abnormalities observed on Day 1, worst case will be presented in table.

The 12-lead ECG results will be summarized for following parameters: heart rate, ECG finding, PR Value, QRS Value, RR Value, QT Value, QTcF Value

Other baseline characteristics will be listed only.

All other screening or day 1 safety assessments will be listed only unless specified differently below.

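### Examination findings are a named safety endpoint, but after baseline they are only listed, so abnormalities not recorded as adverse events get no planned count by arm

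*SAP*

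**What the plan says.** Protocol 3.3.2 and SAP 2.2.2.2 both name as a secondary safety endpoint: "Physical, neurological, ophthalmological, and dermatological examination findings". The safety paragraph of the protocol synopsis (1.1) says: "Evaluation of Safety endpoints will be summarized descriptively by treatment group and visit for the Safety Population".

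The sections that specify the output say something narrower.

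- Protocol 10.11.5: "Abnormal physical examination findings will be listed".
- Protocol 10.11.6: "Abnormal neurological, ophthalmological and dermatological examinations findings will be listed".
- SAP 4.8.3.3, on physical examination: "Abnormal findings occurring after screening and baseline visit (after Day 1) will be listed. No summaries beside baseline are planned".
- SAP 4.8.3.4, on the other three examinations: "Results of such examination will be listed only. No summaries are planned".

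The only examination table in the plan is in SAP 4.3: "Physical examination table will combine results from screening and baseline". SAP 3.4 records no change from the protocol.

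**The concern.** An endpoint that is named in the protocol and measured repeatedly against a concurrent placebo arm would normally be reported so that the arms can be compared. Here the synopsis promises that and the analysis sections withhold it. A reader of the study report could see individual abnormal findings but would not be given the number of patients with a new abnormality on 20 mg, 40 mg and placebo. At stake is how well the placebo comparison is used for one descriptive safety endpoint. No efficacy conclusion depends on it.

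**Working it through.** No formula applies. The check maps each safety endpoint named in protocol 3.3.2 and SAP 2.2.2.2 to the post-baseline output planned for it.

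| Named safety endpoint | Planned post-baseline output | Count or summary by arm? |
|---|---|---|
| Examination findings | Listings (SAP 4.8.3.3, 4.8.3.4) | No |
| Adverse events | Overview with differences in proportions; tables by organ class and preferred term (SAP 4.8.1) | Yes |
| Laboratory | Descriptive statistics, change from baseline, shift tables (SAP 4.8.2) | Yes |
| ECG | Raw values, change, shift and frequency tables (SAP 4.8.3.2) | Yes |
| ESRS | Descriptive statistics of score and change by treatment (SAP 4.8.3.5) | Yes |

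SAP 4.1.2 makes arm the default layout of summary tables, so the laboratory and ECG tables count as by arm. Four of the five endpoints have a post-baseline summary by arm; examination findings do not. The ECG section already plans the kind of output that is missing: "The number of patients with at least one clinically relevant finding detected during the ECG examination will be summarized in frequency tables".

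Next, the four examination types. Physical has one table, at screening and baseline. Neurological, eye and skin have none at any time. Types with a post-baseline table: 0 of 4.

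Next, whether another section fills the gap. Protocol 10.5 has a general rule that categorical data are tabulated by group, but the specific SAP statements exclude it here. The AE route works only for findings recorded as AEs. Protocol 8.3.2 requires a clinically significant laboratory abnormality to be recorded as an AE; protocol 8.3.6 and 8.3.9, on the examinations, contain no matching rule.

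Last, how much there is to read in listings. Post-baseline examinations per patient who completes treatment and attends both follow-up visits (protocol 8.3.6, 8.3.9, 9.14):

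- Neurological: Days 7, 14, 21, 28 and two follow-up visits = 6
- Physical: Day 28 and two follow-up visits = 3
- Eye: Day 28 = 1
- Skin: Day 28 = 1

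The total is 6 + 3 + 1 + 1 = 11. For 165 patients this is at most 165 × 11 = 1,815 examinations. It is a ceiling on examinations performed. It says nothing about how many are abnormal, which the documents do not allow one to estimate.

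**The case against.** The best defence is that listing only is a deliberate choice. The protocol body and the SAP agree on it, and the only text against it is one general sentence in the synopsis. Important findings have other routes. Protocol 8.3.1.1.1 defines an AE broadly enough to cover an unwelcome sign, 8.3.1.2 names physical examination as a source of AEs, and AEs are compared between arms. Movement disorders are scored on the ESRS. What is left should be mainly abnormalities that were present before dosing and did not worsen, or that the investigator did not consider unfavourable. Protocol 8.3.9 also calls the neurological, eye and skin assessments basic. With about 55 patients per arm, listings can be read.

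Most of this stands, and it is why the point is minor. It does not remove the gap: new abnormalities that are not recorded as AEs still have no count by arm.

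Four stronger readings are tempting, and the documents do not support them.

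- A reader might infer that the SAP departs from the protocol's analysis section. It does not; the conflict is between the synopsis and the detailed sections of both documents.
- A reader might infer that examinations alone breach the synopsis sentence. Read literally, that sentence also asks for a visit dimension, and the AE tables in SAP 4.8.1 have none. The contrast that holds is the narrower one: no post-baseline summary by arm of any kind.
- A reader might infer that safety signals would be lost. The AE and ESRS routes make that unlikely for findings of consequence, and no number can be put on the remainder.
- A reader might add that listings show the randomised arm (SAP 4.1.4) while safety analyses go by treatment received (SAP 3.1). That is a general SAP matter, which touches the accepted safety tables equally, and it adds no weight here.

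**Conclusion.** The point holds as a small, inexpensive improvement. A named safety endpoint has no planned post-baseline count by arm, contrary to the synopsis, and neither document explains the difference. The effect is confined to examination abnormalities not recorded as AEs. Its size is unknown, because the documents give neither an abnormality rate nor the share of abnormalities recorded as AEs. The conclusion assumes that the specific SAP statements prevail over the general rule in protocol 10.5, and that the AE and ESRS tables are produced as planned.

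Exempting examinations from the synopsis sentence would remove the contradiction, but the endpoint would still have no comparison with placebo.

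**What to change.** In SAP 4.8.3.3 and 4.8.3.4, add for the Safety Set, by treatment received:

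1. The number and percentage of patients with an abnormal finding at each post-baseline visit at which that examination is scheduled, with patients examined as the denominator. The visits are Day 28 and follow-up for physical; Days 7, 14, 21, 28 and follow-up for neurological; Day 28 for eye and skin.
2. The number and percentage of patients with any abnormality that was absent at the last pre-dose examination and first seen on treatment, counting early-termination examinations. Abnormalities first seen at follow-up are shown separately, for physical and neurological examinations only, because eye and skin are not examined then. Antipsychotics may be resumed from Day 29 (protocol 9.13), which is a reason to keep follow-up apart.

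State treatment received explicitly, since SAP 4.1.2 otherwise defaults to the randomised group. Keep the listings. Allow listing only when fewer than five patients have a new abnormality, as SAP 4.8.3.6 already does for the suicidality scale. Align protocol 10.11.5 and 10.11.6 with the synopsis.

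The cost is a few descriptive tables from examinations already scheduled, plus wording changes. The tables will be sparse and will partly repeat the AE and ESRS tables. The documents do not show whether findings are captured as coded fields or free text, so some coding may be needed.

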4.8.3.5. Extrapyramidal Symptom Rating Scale (ESRS)

ESRS was developed to assess four types of drug-induced movement disorders (DIMD): Parkinsonism, akathisia, dystonia, and tardive dyskinesia. It will be performed once at Screening (Day -10 to -2); once at Baseline (Day -1), once on Day 1, 7, 14, 21 and 28 when start of ratings is to be within 5 minutes before or after 2h post-dose (it will be performed after PANSS, CGI-S, CGI-I and BACS); once during the follow-up visits. A baseline assessment will be performed at Day -1 and repeated on days 7, 14, 21, 28 and follow-up visits. Descriptive statistics of the score and changes from baseline will be presented by treatment and overall in both tabular and graphical form. In case of the latter, boxplots will be used.

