2.3. Summary of Findings from Previous Clinical Studies

2.4. Rationale for the Clinical Study

2.5. Risk-benefit Assessment

Current antipsychotics used in patients with schizophrenia although effective are not perfect as they might be associated with different side effects. The development of new, effective therapy with improved safety profile would be a beneficial treatment options for schizophrenia patients. The PDE10 inhibitors, based on several preclinical models, may represent a new approach for treatment of psychosis. The use of treatment with new mechanism of action may exert some risks, which, based on available information, was recognized and the study was design to minimize it.

In a similar phase 2, randomized, placebo-controlled study, the efficacy and safety of a selective PDE10A inhibitor (TAK-063) in patients with an acute exacerbation of schizophrenia were evaluated [25]. In this study, no clinically relevant or consistent differences were observed between study drug and placebo groups for hematologic, renal, or hepatic lab test results, vital signs, or ECG. Most subjects reported AEs that were mild or moderate in severity, and the AEs reported in this study were generally consistent with the previously conducted phase 1 studies [26, 27]. AEs experienced by ≥5% of subjects in the IMP (TAK-063) group were akathisia (placebo: 4.9%; IMP: 13.3%), somnolence (placebo: 2.5%; IMP: 12.0%), dyspepsia (placebo: 7.4%; IMP: 10.8%), headache (placebo: 11.1%; IMP: 7.2%), nausea (placebo: 6.2%; IMP: 6.0%), dystonia (placebo: 1.2%; IMP: 6.0%), and decreased appetite (placebo: 1.2%; IMP: 6.0%). None of the serious adverse event (SAE) was considered related to study drug. The investigated PDE10A inhibitor did not result in any deaths, and most AEs were mild or moderate in severity and did not result in the specific study discontinuation [26, 27].

Phase I study results in healthy volunteers showed that CPL500036 compound is generally safe and well tolerated. Potential risks associated with use of CPL500036 based on most frequently AE occurrence in phase I study, assessed as related or possible related with IMP:

- Drowsiness/somnolence,
- Feeling calm,
- Headache,
- Sensation of cold,
- Sensation of hot/heat.

The intensity of observed AEs was classified as mild or moderate. All the AEs were transient and their frequency decreased after Day 3 of administration (in multiple dosing). The most

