4.2. Scientific Rationale for the Study Design

This study evaluates the efficacy, safety, tolerability and PK of 2 different doses of CPL500036 (PDE10A inhibitor) in patients with an acute exacerbation of schizophrenia. The design is standard and is considered appropriate to meet the objectives of the study.

The study design meets the recommendations provided in the "Guideline on clinical investigation of medicinal products, including depot preparations in the treatment of schizophrenia" (EMA/CHMP/40072/2010 Rev. 1, 30). This is a proof-of-concept study assessing CPL500036 compound with new mechanism of action in treating positive symptoms of schizophrenia so comparison to placebo is considered appropriate to assess treatment benefit. To better characterize the effect size two doses of CPL500036 as monotherapy will be used. Risks in the study, especially those of using placebo were acknowledge and the study was design to minimize it (see section 2.5). For efficacy assessment validated scales recommended in the guideline are to be used as an assessment tools. PANSS will be used for primary endpoint measurements, including the recommended definition of responders used in short term trials with acute/exacerbated symptoms is to be used for clinical response evaluation. For secondary efficacy measures both CGI-S and CGI-I assessments are planned in the study. Extrapyramidal symptoms (EPS) are potential adverse events that according to guideline are to be monitored during the studies in schizophrenia patients, which was addressed by using ESRS scale for EPS monitoring.

The safety assessments for the study are accepted measures for ensuring safety of subjects during a clinical trial. The PK sampling schedule is considered appropriate given the information available. The rationale for dose selection is discussed in Section 4.3.

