2.4. Sample size

This proof-of-concept study is powered to rule out an effect size of 0.5 or greater for the primary endpoint. With 50 patients per group, the study has 80% power to detect an effect size of 0.5 or greater for 1 of the 2 dose groups, compared to placebo, given a 2-sample t-test, and a 2-sided 10% significance level. Each dose will be compared to placebo, without adjustment for multiplicity so the type-I error will be slightly inflated, however, as this is a proof-of-concept study, the slight inflation is acceptable. Assuming an approximately 10% of patients may drop out, approximately 165 patients will be randomized (55 patients per group).

3. General aspects of the statistical analysis

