4.1.1.11. Extrapyramidal Symptom Rating Scale (ESRS)

The Extrapyramidal Symptom Rating Scale (ESRS) was developed to assess four types of drug-induced movement disorders (DIMD): Pakinsonism, akathisia, dystonia and tardive

dyskinesia (TD). It will be performed once at Screening (Day -10 to -2); once at Baseline (Day -1), once on Day 1, 7, 14, 21 and 28 when start of ratings is to be within 5 minutes before or after 2h post-dose (it will be performed after PANSS, CGI-S, CGI-I and BACS); once during the follow-up visits. A baseline assessment will be performed at Day -1 and repeated on days 7, 14, 21, 28 and follow-up visits. The ESRS consists of four subscales and four CGI-S scales:

- A questionnaire of EPS or DIMD (part I),
- An examination of Parkinsonism and akathisia (part II),
- An examination of dystonia (part III),
- An examination of dyskinesia (part IV),
- Clinical global impression severity (CGI-S) scales of tardive dyskinesia, Parkinsonism, dystonia and akathisia (part V – part VIII).

Total score for DIMD (Chouinard, G., Margolese, H.C., 2005) is formed based on all 41 items of the ESRS (part I – part IV), while CGI-S's are analyzed as separate items (part V – part VIII).

For the subjective examination (subscale I of the ESRS) scoring is on a 4-point scale (from 0 to 3). Rest of the DIMD examination (part II – part IV) is scored on a 7-point scale (from 0 to 6). Total score for DIMD is sum of the all 41 items from part I to part IV. For more details about scoring please refer to the table below.

Table 3. ESRS scoring

ESRS Part	Symptom	Scoring
Part I		Absent = 0
		Mild = 1
		Moderate = 2
		Severe = 3
Part II	Tremor	None = 0
		Borderline, occasional = 1
		Small amplitude, occasional = 2
		Small amplitude, frequent = 3
		Small amplitude, constant or almost so = 4
		Moderate amplitude, occasional = 3
		Moderate amplitude, frequent = 4
		Moderate amplitude, constant or almost so = 5
		Large amplitude, occasional = 4
		Large amplitude, frequent = 5
		Large amplitude, constant or almost so = 6
	Bradykinesia	Normal = 0
	,	Global impression of slowness in movements = 1
		Definite slowness in movements = 2
		Very mild difficulty in initiating movements = 3
		Mild to moderate difficulty in initiating movements = 4
		Difficulty in starting or stopping any movement, or freezing on initiating voluntary act
		= 5
		Rare voluntary movement, almost completely immobile = 6
	Gait and Posture	Normal = 0
		Mild decrease of pendular arm movement = 1

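### The ESRS is reported only as scores, changes and boxplots: no count of patients who worsened, no shift table, and no between-arm difference with a confidence interval for extrapyramidal effects

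*SAP*

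**What the plan says.** ESRS monitoring is a safety endpoint in Protocol 3.3.2 and SAP 2.2.2.2. Protocol 4.2 gives the reason, "Extrapyramidal symptoms (EPS) are potential adverse events that according to guideline are to be monitored during the studies in schizophrenia patients", and names the ESRS as the means of doing so. Ratings are planned at screening, Day -1, Days 1, 7, 14, 21 and 28, and follow-up.

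For analysis, Protocol 10.11.6 says "Descriptive statistics of the score and change from baseline will be summarized at each scheduled time point for extrapyramidal side effects". SAP 4.8.3.5 says "Descriptive statistics of the score and changes from baseline will be presented by treatment and overall in both tabular and graphical form" and specifies boxplots for the graphs. SAP 4.1.1.11 defines the main score: "Total score for DIMD is sum of the all 41 items from part I to part IV". The same section has the four global severity ratings (tardive dyskinesia, parkinsonism, dystonia, akathisia) analysed separately from that total.

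SAP 4.8.1 tabulates treatment-emergent adverse events by system organ class and preferred term as numbers and percentages of patients. It gives differences in proportions with Agresti-Caffo 95% intervals for a fixed list of overview categories, and extrapyramidal effects are not on that list. Laboratory, vital-sign, ECG and C-SSRS data all get shift tables (SAP 4.8.2, 4.8.3.1, 4.8.3.2, 4.8.3.6). The ESRS does not.

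Protocol 2.5 reports, in per cent, from an earlier phase 2 trial of another PDE10A inhibitor: "akathisia (placebo: 4.9%; IMP: 13.3" and "dystonia (placebo: 1.2%; IMP: 6.0".

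**The concern.** Drug-induced movement effects of the cited size affect a minority of patients and may be present at one weekly rating and gone at the next. Summaries by visit of a score do not answer the plain safety question of how many patients in each arm got worse at any time on treatment, and by how much that differs from placebo. Three features weaken the planned display:

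- Medians, quartiles and boxes respond little when few patients are affected.
- The 41-item total adds four disorders together, so an effect in one is diluted.
- Each visit is summarised alone, so patients affected at different visits are never added up.

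The preferred-term rows give incidence. However, under Protocol 8.3.1.2 they rest on spontaneous reports, findings at examination and an open question, not on the structured rating chosen for this risk. What is at stake is how clearly the trial can report on a risk that it set out to monitor.

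**Working it through.** **The plan's own figure.** The documents give no figure for the ESRS or for extrapyramidal effects. The planning figure that enters here is the arm size: "approximately 165 patients will be randomized (55 patients per group". Its basis reproduces. With 50 per group, effect size 0.5 and two-sided 10%, 0.5 × √(50/2) − 1.645 = 0.855, and Φ(0.855) = 80.4% (79.9% with the noncentral t), against the stated 80%.

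**Inputs from the documents.** n = 55 per arm (SAP 2.4). Akathisia 13.3% versus 4.9% and dystonia 6.0% versus 1.2% (Protocol 2.5; these are adverse event rates). On-treatment ratings on Days 1, 7, 14, 21 and 28.

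**Assumptions not in the documents.** The share of patients with a non-zero rating equals the cited adverse event rate, and all others score 0. Affected patients average 3 (SD 0.8) on a 0–6 item. The background SD of the total score is taken from 1 to 5.

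**Step 1. Expected patients per arm.**
- Akathisia: 55 × 0.133 = 7.3 versus 55 × 0.049 = 2.7.
- Dystonia: 55 × 0.060 = 3.3 versus 55 × 0.012 = 0.7.

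**Step 2. Does the box move?** With 55 patients the upper quartile is 0 if at most 13 are non-zero. For X ~ Binomial(55, 0.133), P(X ≤ 13) = 98.9%. For dystonia (0.060) it exceeds 99.99%. The median is 0 with probability above 99.99% in both cases.

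**Step 3. What would still show?** With both quartiles at 0, every non-zero patient is drawn as an outlier point (SAP 4.1.3) and enters the maximum (SAP 4.1.2). The chance of at least one such patient in an active arm is 1 − 0.867^55 = 99.96% for akathisia and 1 − 0.940^55 = 96.7% for dystonia. The chance in the placebo arm is 93.7% and 48.5%, so the presence of points alone does not separate the arms well.

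**Step 4. The mean, on one item and on the total.** The mean difference is 3 × (0.133 − 0.049) = 0.25 for akathisia and 3 × (0.060 − 0.012) = 0.14 for dystonia. On a single item the SDs are 0.89 and 0.57, giving standardised differences of 0.28 and 0.25, and power of 44% and 37% at two-sided 10%. On the total, background variation is added. For akathisia the SD becomes √(0.89² + background²):

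| Background SD | Akathisia: standardised difference (power) | Dystonia: standardised difference (power) |
|---|---|---|
| 1 | 0.19 (26%) | 0.13 (16%) |
| 2 | 0.12 (15%) | 0.07 (10%) |
| 3 | 0.08 (11%) | 0.05 (8%) |
| 5 | 0.05 (8%) | 0.03 (7%) |

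**Step 5. By visit.** As an extreme illustration, suppose each of the 7.3 akathisia patients is affected at only one of the five ratings, spread evenly. Each visit then shows 7.3/5 ≈ 1.5 patients, or about 2.7% of 55, while the cumulative figure is 13.3%.

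**Step 6. What a count of patients would give.** The Agresti-Caffo method adds one event and one non-event to each arm.
- Akathisia, expected counts: (7.315 + 1)/57 − (2.695 + 1)/57 = 0.146 − 0.065 = 0.081. The standard error is √[(0.146 × 0.854 + 0.065 × 0.935)/57] = 0.057, so the 95% interval is −3.1 to +19.3 percentage points.
- Whole numbers of patients: akathisia 7 versus 3 gives +7.0 (−4.2 to +18.2); dystonia 3 versus 1 gives +3.5 (−4.7 to +11.7).
- Power at two-sided 10%, akathisia: (0.084 − 1.645 × 0.0548)/0.0543 ≈ −0.11, or 45%. Dystonia: 38%. Fisher's exact test gives 34% and 14%. For 80% power, 144 and 186 patients per arm would be needed.

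**The case against.** A reader might infer that extrapyramidal effects are analysed only through ESRS scores, so that an excess of the cited size would be almost invisible. The documents do not support that reading:

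- The preferred-term tables in SAP 4.8.1 give akathisia and dystonia incidence. The rates cited in Protocol 2.5 are themselves adverse event rates, so the like-for-like display is already planned.
- Protocol 5.4.3 requires the adverse event behind any use of benzatropine, biperiden or propranolol to be recorded, so an episode treated between ratings is still captured. Concomitant drugs are counted by ATC level (SAP 4.5).
- The four global ratings are analysed separately, so akathisia and dystonia are not seen only through the total.
- Outlier points and maxima would show cases (step 3).
- No document says that ESRS scores are mostly zero. Patients are acutely ill and may be fresh from washout, and the akathisia item already scores 1 for looking restless (SAP Table 3).
- On a single item, a comparison of means has about the same power as a count (44% versus 45%), so zeros alone hide nothing in a mean.

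All of this stands, and it limits the point. It does not close the gap. The adverse event rows are split by term, are not pooled and carry no interval. The ATC table is not by indication, so propranolol given for akathisia may share a row with the other beta-blockers that Protocol Table 9 allows for hypertension. Neurological examinations are only listed (SAP 4.8.3.4). Points and maxima show that cases exist at a visit, not how many patients were ever affected.

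**Conclusion.** The point holds as a gap in presentation. The scale that the protocol names for monitoring this risk yields no cumulative count of patients, no shift table and no estimate against placebo, although the other main safety measures get at least shift tables. At the cited rates, and if non-zero ratings are as uncommon as those rates, median, quartiles and box would almost certainly not move. A single-domain effect would shrink to 0.05–0.19 SD (akathisia) on the 41-item total for the background SDs assumed.

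Those sizes rest on the assumed share of non-zero ratings, the severity of affected patients and the background SD, none of which the documents give. They do not show that the trial would miss an excess, because the adverse event tables remain. Nor would a count turn this into a powered comparison: power is about 45% at most. The change is worth making because it is cheap and gives an estimate for each patient across visits that nothing else in the plan provides.

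**What to change.** Add one table to SAP 4.8.3.5, by arm, for the safety set: the number and percentage of patients with any worsening from Day -1, at any rating from Day 1 to Day 28, in each of the four ESRS global ratings (akathisia, dystonia, parkinsonism, tardive dyskinesia). Give each dose's difference from placebo with the Agresti-Caffo 95% interval of SAP 4.8.1. Show patients given benzatropine, biperiden or propranolol for these effects, either in a separate row or in a row combined with worsening. Keep the score summaries and boxplots. State that the table is for estimation.

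The cost is one extra table from data already collected; Protocol 10.9 lists the indication for each concomitant drug. The drawback is that any worsening includes borderline one-step changes, which will add noise in all arms.
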